5.2.1 Discontinuation from the study

Patients must be discontinued from the study for any of the following reasons:

- Withdrawal of informed consent.
- Discontinuation is considered to be in the interest of the patient from a safety perspective as judged by the Investigator.
- Positive or unclear pregnancy test.
- The Sponsor or Investigator terminates the study or the study terminates at a particular investigational site. If the Sponsor or the Investigator decides to prematurely terminate the study, the patient will be promptly informed. The investigational site/head of the medical institution should report the fact and the reason in writing to the IRB / IEC.
- Patient has to undergo open surgical AAA treatment or AAA endovascular repair (as per the treating physician's decision based on the standard of care as documented in the Guidelines for Diagnosis and Treatment of Aortic Aneurysm and Aortic Dissection¹).
- The patient experiences a rupture of his/her AAA.
- Patient becomes an employee of the investigational site, a tobacco company or any other parties involved in the study.
- Lost to follow-up.

Patients may be discontinued from the study for the following reasons:

- Non-compliance to the study procedures based on the judgment of the Investigator.

If a violation of selection criteria is detected after enrollment, patients might be discontinued from the study based on a case-by-case decision of the Investigator.

Confidentiality Statement

Data and information contained in this document are considered to constitute trade secrets and confidential commercial information, and the legal protections provided to such trade secrets and confidential information are hereby claimed under the applicable provisions of applicable law. No part of this document may be publicly disclosed without the written consent of Philip Morris Products S.A.

Patients will not be discontinued from the study for the use of tobacco or nicotine-containing products other than their assigned product/regimen unless judged by Investigator.

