3.4 Additional Endpoints

Throughout the course of the study, several amendments to the protocol were issued with updates on some of the objectives or endpoints considered. The following endpoints have been collected up to the issuances of these amendments (note that subjects were enrolled only after protocol version 4 was issued):

Amendments	Endpoint
Protocol version 6	
Part of the Selected clinical risk endpoints (CREs) in Secondary Objectives and Endpoints are collected up to the amendments.
 
• Hemoglobin A1c (HbA1c)• Total Antioxidant Capacity (TAC)• Metalloproteinase (MMP) 2 and 9
Protocol version 7	
Secondary Objectives and Endpoints below are collected up to the amendments.
 
• Co-morbidities• CREs
◦ High sensitive C-reactive protein (hs-CRP)◦ Low density lipoprotein (LDL)◦ High density lipoprotein (HDL)◦ Total Cholesterol (TC)*◦ Triglyceride (TG)*◦ Fasting blood glucose*◦ White blood cell (WBC)*◦ Platelet counts*◦ D-dimer◦ Fibrinogen◦ 11-dehydro-thromboxane B2 (11-DTX-B2)◦ 8-Epi Prostaglandin F2 Alpha (8-epi-PGF_{2α})◦ Soluble inter-cellular adhesion molecule-1 (sICAM-1)◦ Apolipoprotein A1 (Apo A1)◦ Apolipoprotein B (Apo B)◦ Homocysteine in the respective body matrix• Ankle-brachial index (ABI)• Assessment of Transcriptomic, Proteomic, and Lipidomic Profiles
◦ Transcriptomic, proteomic and lipidomic profiles assessment derived from blood samples◦ Lipidomic profile assessment in urine

Confidentiality Statement

Data and information contained in this document are considered to constitute trade secrets and confidential commercial information, and the legal protections provided to such trade secrets and confidential information are hereby claimed under the provisions of applicable law. No part of this document may be publicly disclosed without the written consent of Philip Morris Products S.A.

The data related to these endpoints will be listed and summarized in AAA patients who switch from smoking CIG to using IQOS, patients who continue to smoke CIG, and patients who had stopped smoking.

* Note that TC, TG, fasting blood glucose, WBC, and platelet counts are still part of the objective related to safety monitoring. These will be analyzed as part of that objective and not considered here as additional endpoints.

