5.7 Product Use Categories

In addition to enrolled arms, subjects will be classified by product use categories. These will be defined based on the monthly average number of nicotine-containing products as self-reported in the diary.

More specifically, monthly for each subject, the average number over the entire month of cigarettes per day, IQOS per day, heat-not-burn products other than IQOS per day, e-cigarettes per day, smokeless tobacco pipe per day, smokeless tobacco per day, cigars/pipes/kiseru/shisha per day, and nicotine replacement therapy per day, will be determined as follows:

- If the subject answers 'every day' to the initial question related to a nicotine-containing product type, the number of days of use is set to 30. If the subject answers 'not at all' to this question, then the number of days of use is set to 0. If the subject answers 'some days', the number of days of use is set to the answer provided by the subject to the subsequent question on how many of the past 30 days the subject has used the product.
- The number of days of use is then multiplied by the number provided as answer to the question on the average number of products used per day by the subject (if the subject has 0 day of use, the subject does not need to answer that question and the average number of products used can be set to 0). The result of this multiplication is then divided by 30 to get an estimate of the average number of products used per day over the entire month.
- If the number of days is missing, or if it is not equal to 0 but the average number of products per day is missing, then the average number of products used per day over the entire month is set to missing.

Once the average number of products used per day over the entire month will be determined, all the available (out of 6) monthly averages collected between V2 and V3 will be summed up and divided by the number of non-missing monthly averages, and the result of this calculation

Confidentiality Statement

Data and information contained in this document are considered to constitute trade secrets and confidential commercial information, and the legal protections provided to such trade secrets and confidential information are hereby claimed under the provisions of applicable law. No part of this document may be publicly disclosed without the written consent of Philip Morris Products S.A.

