will be assigned to V3 and represent the average number of products used per day over the previous 6 months. Similarly, all the available (out of 6) monthly averages collected between V3 and V4 will be summed up and divided by the number of non-missing monthly averages, and the result of this calculation will be assigned to V4. The process is repeated to obtain estimates of average number of products used per day over the previous 6 months for V5, V6, V7, and V8. If none of the 6 previous monthly averages is available, the average number of products used per day over the previous 6 months will be set to missing.

If a subject terminates the study early between V_i and V_{i+1} (where i represents any number between 2 and 7), the average number of products used per day over the previous 6 months will be set to missing at V_{i+1} .

For each subject, the following table will be filled, where each cell represents an average number of products used per day over the previous 6 months:

Product	V3	V4	V5	V6	V7	V8
Cigarettes/Roll-your-own cigarettes	Cig3	Cig4	Cig5	Cig6	Cig7	Cig8
IQOS	IQ3	IQ4	IQ5	IQ6	IQ7	IQ8
Heat-not-burn other than IQOS	HnB3	HnB4	HnB5	HnB6	HnB7	HnB8
E-cigarettes	EC3	EC4	EC5	EC6	EC7	EC8
Smokeless tobacco pipes	Stp3	Stp4	Stp5	Stp6	Stp7	Stp8
Smokeless tobacco	St3	St4	St5	St6	St7	St8
Cigars/Pipes/Kiseru/Shisha	Cpk3	Cpk4	Cpk5	Cpk6	Cpk7	Cpk8
Nicotine replacement therapy	Nrt3	Nrt4	Nrt5	Nrt6	Nrt7	Nr8

Using this table, the product use category for any subject will be determined as follows:

- A subject will be classified in the smoking abstinence product use category if all $Cigx < 1$, $IQx < 1$, $HnBx < 1$, $ECx = 0$, $Stpx = 0$, $Stx = 0$, $Cpk3 = 0$ for all $x = 3, 4, 5, 6, 7$, and 8 .
- A subject will be classified in the IQOS product use category if all $Cigx < 1$, $IQx \geq 1$, $HnBx < 1$, $ECx = 0$, $Stpx = 0$, $Stx = 0$, $Cpk3 = 0$ for all $x = 3, 4, 5, 6, 7$, and 8 .
- A subject will be classified in the CIG product use category if all $Cigx \geq 1$, $IQx < 1$, $HnBx < 1$, $ECx = 0$, $Stpx = 0$, $Stx = 0$, $Cpk3 = 0$ for all $x = 3, 4, 5, 6, 7$, and 8 .
- A subject will be classified in the dual-use product use category if all $Cigx \geq 1$, $IQx \geq 1$, $HnBx < 1$, $ECx = 0$, $Stpx = 0$, $Stx = 0$, $Cpk3 = 0$ for all $x = 3, 4, 5, 6, 7$, and 8 .

Confidentiality Statement

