Data and information contained in this document are considered to constitute trade secrets and confidential commercial information, and the legal protections provided to such trade secrets and confidential information are hereby claimed under the provisions of applicable law. No part of this document may be publicly disclosed without the written consent of Philip Morris Products S.A.

- A subject will be classified in the ‘other’ product use category in all other cases not mentioned above.

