9.1.5 Handling of Dropouts or Missing Data

For BoExp parameters:

- Values below the lower limit of quantification (LLOQ) will be imputed using LLOQ/2. For values above the upper limit of quantification (ULOQ), the ULOQ will be imputed.
- The number and percentage of values below LLOQ or above ULOQ will be presented in each summary table (the percentage of values below LLOQ/ULOQ will use the number of patients with non-missing values in the denominator). If more than 50% of the data are below LLOQ, only the number and percentage of values below LLOQ will be reported in the summary together with the minimum and maximum values.

For self-reported tobacco or nicotine-containing product use:

- Only available data will be included in the product use summaries.

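### As written, SAP 5.7 puts every patient who leaves before V8 in 'other', so the repair and rupture outputs by product use category depend on the outcome they tabulate

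*SAP*

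**What the plan says.** SAP 5.7 builds one cell per product and visit from the monthly diary. One usable month is enough: the V3 cell averages all "the available (out of 6) monthly averages collected between V2 and V3", and later visits follow the same pattern. Two rules produce missing cells. When a subject terminates early between two visits, the average "over the previous 6 months will be set to missing at" the next visit. "If none of the 6 previous monthly averages is available", the cell is missing as well.

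The four named categories then set conditions on seven products. For example, "A subject will be classified in the IQOS product use category if all" of a list of conditions hold at every visit from V3 to V8. Each list requires zero use of e-cigarettes, smokeless tobacco pipes and smokeless tobacco (ECx, Stpx, Stx). The cigar/pipe/kiseru/shisha term is printed as Cpk3 in all four lists, while every other term carries x. Whatever meets none of the four goes to the 'other' "product use category in all other cases not mentioned above".

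Protocol 5.2.1 lists reasons for which a patient must be discontinued. One is the need for open or endovascular repair; another is "The patient experiences a rupture of his/her AAA". SAP 9.5.2.1.1 (Kaplan-Meier) and SAP 9.5.2.1.2 (person-year incidence) plan repair and rupture outputs on the FAS, by study arm and by product use category.

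**The concern.** Category membership requires data up to V8, and the events being tabulated end participation. A patient who used only IQOS throughout and had a repair decision at 20 months leaves the study, has no V6 to V8 cells, and is counted in 'other'. The same holds for cigarette smokers, dual users and abstainers.

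At stake is how the by-category tables will be read. SAP 3.5.2 says the study is meant to inform on complete switching and that dual use will be examined. The arms ignore actual use, so the category analyses announced in SAP 4.3.3 are the route to that. As written, repair and rupture would look almost absent in all four named categories and would collect in 'other', because of the classification rule and not because of product use.

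**Working it through.** The plan gives no event rate or figure for this point, so there is nothing to reproduce. The check has three parts.

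**1. The rule.** Take four constant-use patterns (abstinent, IQOS only, CIG only, dual) and let the patient exit in each of the six intervals between V2 and V8: 4 × 6 = 24 profiles.

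- A missing cell fails every condition: 24 of 24 go to 'other'.
- SAS ordering (missing < 1 is true; missing = 0 and missing ≥ 1 are false): 24 of 24 go to 'other', because ECx = 0, Stpx = 0 and Stx = 0 fail.
- Missing visits ignored (not stated in the SAP): 20 of 24 keep their category. Only the 4 that exit before V3 go to 'other'.

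**2. Incidence.** Assumptions: risk p per 6-month interval, constant and the same for everyone; a share f of decisions made at visits; exit on the decision or rupture date.

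- True rate: p / 0.5 = 2p per year.
- A named category holds only V8 completers. Its only possible events are those decided at V8 itself: about f × p over 3 years, or f × p / 3 per year.
- Ratio: (f × p / 3) / (2p) = f / 6. This is 0 at f = 0, about 8% at f = 0.5 and 1/6 (17%) at f = 1. Exact values for p from 0.015 to 0.075 are 0, 0.084 to 0.085, and 0.167.
- If instead every repair decided after V7 is recorded at an attended V8, the category keeps one interval's decisions out of six: (p / 3) / (2p) = 1/6.

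The counterpart is an inflated rate in 'other'. For illustration, assume annual event rate λ = 0.05, other dropout d = 0.05 per year, T = 3 years, and 'other' holding only early exits. With h = λ + d = 0.10, mean time to exit among those who leave is 1/h − T·e^(−hT)/(1 − e^(−hT)) = 10 − 8.57 = 1.43 years. The rate in 'other' is (0.05/0.10)/1.43 = 0.35 per person-year, against a true 0.05. With λ from 0.03 to 0.20 and d from 0 to 0.10 it runs from 0.17 to 0.74.

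**3. Kaplan-Meier.** SAP 9.5.2.1.1 counts time from diagnosis, in months of 30.4375 days, and reports estimates at 6, 12, 18, 24, 30 and 36 months. Inputs: at least 20 weeks (140 days) between two post-diagnosis CT scans (Protocol 5.1.1); at least 1 day from V1 to V2; visits every 6 months, each up to 14 days early relative to the previous one (Protocol 9.3); 30-day months. SAP 3.4 reports "note that subjects were enrolled only after protocol version 4 was issued". The criteria of earlier versions are not shown, so a zero gap is the lower bound.

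Time to a visit = (gap + 1 + 30 × months − days early + 1) / 30.4375.

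| Gap from diagnosis to V1 | Visits | V7 (month 30) | V8 (month 36) |
|---|---|---|---|
| 140 days | on schedule | 1042/30.4375 = 34.2 | 1222/30.4375 = 40.1 |
| 140 days | all 14 days early | 972/30.4375 = 31.9 | 1138/30.4375 = 37.4 |
| 0 days | on schedule | 902/30.4375 = 29.6 | 1082/30.4375 = 35.5 |
| 0 days | all 14 days early | 832/30.4375 = 27.3 | 998/30.4375 = 32.8 |

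If exit coincides with the event date, named-category curves are at 100% up to V8: all six time points with the 140-day gap, and 6 to 30 months with no gap. If a repair decided between V7 and V8 can be recorded at an attended V8, they are certain to be at 100% only up to V7: 6 to 30 months with the 140-day gap, and 6 to 24 months with none.

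**The case against.** **Intent.** SAP 9.1.5 says "Only available data will be included in the product use summaries", under a heading on dropouts and missing data, and SAP 9.4 places a listing of categories among the product use outputs. The authors may have meant to classify on attended visits. But the sentence governs summaries, not classification, and nothing in SAP 5.7, 7, 8.1 or 9.1.5 says that early exits are classified on attended visits. Intent stays open; the written rule does not.

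**Exit date.** A reader might infer that the named categories are event-free at all six time points in any case. The documents do not support that. Repair is dated by the decision, no text dates the discontinuation, and Protocol Appendix 1 has the decision date recorded at V3 to V8. A repair decided after V7 and recorded at an attended V8 leaves the V8 cell intact. This objection stands, and the sizes are conditional on it.

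**Cells.** A reader might also infer that any blank among 7 × 6 = 42 cells sends a subject to 'other'. That holds only if a missing cell fails every test. The protocol names SAS, where missing passes a 'less than 1' test. The cells that must then be present, reading Cpk3 as Cpkx, number 24 for abstinence, 30 for IQOS, 30 for CIG and 36 for dual use. Early exits fail either way.

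**Time origin.** Part of the early flatness has nothing to do with SAP 5.7. Time runs from diagnosis in patients who were event-free at enrollment, and the LIFETEST code has no delayed entry, so the by-arm curves share it. This stands.

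**Importance.** The outputs are additional and descriptive, 32 patients were enrolled when the decision to stop recruitment was described, and event listings are planned. This limits the consequences but does not make the tables right.

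**Conclusion.** The concern holds on the text. Under SAP 5.7 as written, an event that ends participation before V8 cannot appear in the abstinence, IQOS, CIG or dual-use category and is counted in 'other'. That needs no assumption about event rates.

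The size does rest on assumptions. With exit on the event date and constant risk, named categories show 0 to about 1/6 of the true incidence, and their curves stay at 100% up to V8. With late repair decisions recorded at V8, flatness is certain only up to V7, about 34.2 months after diagnosis with a 140-day gap on schedule, or 31.9 with every visit early.

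The limits are clear. By-arm outputs do not use SAP 5.7. The rule treats IQOS and CIG alike, so an inference that it favors one product is not supported. 'Other' is not a pure event group: it also takes dropouts without an event, completers with a whole 6-month interval of missing diaries, and patients who change product.

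The Cpk3 term is a separate and probably clerical point. Coded literally, cigar, pipe, kiseru or shisha use after V3 is never tested.

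**What to change.** (a) **SAP 9.5.2.1.1 and 9.5.2.1.2.** Omit the repair and rupture outputs by product use category, and rely on the by-arm outputs and the planned listing, noting that by-arm time from diagnosis includes a period before enrollment in which no event could be observed. If the by-category outputs are kept, assign category only from product use before the event, for example the V3 category in patients still event-free and in the study at V3, with time counted from V3. Label this as supplementary to the time-from-diagnosis endpoint.

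(b) **SAP 5.7, for the other by-category outputs.** Apply each rule to completed intervals with values for all seven tested products, report subjects with no such interval as unclassifiable and not as 'other', and show the full V3 to V8 rule as a sensitivity table. This alone does not repair the event outputs, because category would still be set by product use during follow-up.

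(c) **SAP 5.7.** Replace Cpk3 with Cpkx in all four rules.

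Cost: wording and derivation code, no new data. A V3 start leaves earlier events out of the by-category results; they remain in the by-arm outputs and the listing. Under (b), patients with shorter follow-up meet a named category more easily, which the sensitivity table makes visible.

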6 SAMPLE SIZE JUSTIFICATION

The sample size of patients is not based on a statistical hypothesis, as this is a descriptive study, designed to characterize the growth rate of AAA and the progression of disease, to better understand the impact of IQOS relative to CIG on the progression of disease. Patients will be enrolled/randomized per study arm.

7 CHANGES FROM THE PROTOCOL SPECIFIED STATISTICAL ANALYSES

Stratified analyses were planned in the protocol. However, after taking into account the sample size, the expected number of subjects in each stratum will be too small to draw any conclusion. Thus, stratified analyses will not be conducted.

Transcriptomic, proteomic and lipidomic profiles will not be evaluated and only some of those data which are collected with other laboratory parameters will be provided in the listings.

Table 3 of the Clinical Study Protocol (CSP) contains a footnote stating that ‘the albumin to creatinine ratio will be used to evaluate potential microalbuminuria’. This ratio will not be evaluated since albumin is not measured in urine, but only in blood; and computing the ratio based on blood measurements cannot be used to evaluate potential microalbuminuria.

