Confidentiality Statement

Data and information contained in this document are considered to constitute trade secrets and confidential commercial information, and the legal protections provided to such trade secrets and confidential information are hereby claimed under the applicable provisions of applicable law. No part of this document may be publicly disclosed without the written consent of Philip Morris Products S.A.

Besides its role as the most important risk factor for developing AAA, smoking also significantly accelerates the growth of an AAA. The growth rate observed in CC smokers is higher than it is in former CC smokers (an increase of approximately 0.4 mm/year)^{12,13}. Through the impact on growth rate, CC smoking also increases the risk of an AAA rupture and decreases the time to AAA open surgical/endovascular repair intervention^{13,14}. Furthermore, a larger aneurysm size at diagnosis indicates a more rapid expansion of the aneurysm further on and therefore a faster disease progression¹⁰. Abdominal Aortic Aneurysms that reach a diameter of ≥ 55 mm in males or ≥ 50 mm in females, as well as AAA that have a growth rate of ≥ 5 mm within 6 months are common indicators for open surgical interventional treatment or AAA endovascular repair of the AAA¹.

Philip Morris International (PMI) develops, assesses and commercializes a portfolio of innovative products intended to (1) significantly reduce the risk of smoking-related disease compared to continued smoking of CC and (2) are accepted by smokers as substitutes for CC.

More than 6000 smoke constituents have been identified when the tobacco is burned or combusted¹⁵, and more than 100 of them have been categorized as harmful and potentially harmful constituents (PHHCs)¹⁶. Lowering the temperature and heating the tobacco instead of burning it can substantially reduce levels of PHHCs. PMI's Tobacco Heating System (THS, marketed under the brand name of IQOS) is a novel tobacco heating system that heats a specifically designed tobacco stick (*HeatStick*) within a precisely controlled temperature range (far lower temperatures than CC) rather than burning it. IQOS replicates the ritual of smoking but without combustion.^{15,16}.

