This selection of stratification criteria is based on: 1) the size and AAA growth rate prior to stopping smoking have been shown to affect incidence of open surgical AAA treatment or AAA endovascular repair or AAA rupture and 2) sex differences in terms of growth rate and indication for open surgical AAA treatment or AAA endovascular repair as well as for the risk of rupture exist.

The choice of the primary and secondary objectives are based on 1) the standard of care procedures with regards to AAA diagnosis and follow-up as described in the Guidelines for Diagnosis and Treatment of Aortic Aneurysm and Aortic Dissection^{1, 2}, 2) the most clinically relevant endpoints, i.e., AAA diameter and AAA growth within 6 - 12 months' time periods.

Although there is evidence that SC alters the growth rate of AAA and therefore seems to delay the time to open surgical AAA treatment or AAA endovascular repair and AAA rupture, the data available in the literature for AAA growth rates in Japanese patients who continue to smoke CC and patients who had stopped smoking are still scarce. Therefore, the assessment of these parameters as primary and secondary endpoints will thus provide insight on the effect of IQOS on these endpoints in comparison to continued smoking as well as on the effect of SC.

Confidentiality Statement

Data and information contained in this document are considered to constitute trade secrets and confidential commercial information, and the legal protections provided to such trade secrets and confidential information are hereby claimed under the applicable provisions of applicable law. No part of this document may be publicly disclosed without the written consent of Philip Morris Products S.A.

Cardiovascular risk factors will serve to support understanding of the respective effects of continued smoking, stopping smoking or switching to IQOS on the clinically relevant endpoint of AAA growth.

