12.1.1 Stratification Criteria

For the primary analysis of AAA annual growth rate, the following stratification criteria will be used:

- Aortic maximum-minor-axis diameter (male patients: < 40 mm and \geq 40 mm; female patients: < 35 mm and \geq 35 mm, using the CT scan made at V1 and assessed by the central reading site
- Sex (male vs. female)

Although smokers who had stopped smoking will be enrolled in the SC arm without randomization, they will be analyzed based on the defined stratification criteria. Additional stratified presentations (e.g., pack years of history of smoking) may be defined in the SAP.

Confidentiality Statement

Data and information contained in this document are considered to constitute trade secrets and confidential commercial information, and the legal protections provided to such trade secrets and confidential information are hereby claimed under the applicable provisions of applicable law. No part of this document may be publicly disclosed without the written consent of Philip Morris Products S.A.

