12.6 Primary Analysis

The primary analysis will be a descriptive analysis of patients who were randomized to IQOS use as compared to patients who were randomized to continue to smoke CC (IQOS arm versus CC arm) in the Full Analysis Set of AAA patients.

The primary endpoint is the comparison of the annualized mean growth rates in patients diagnosed with AAA between patients who were randomized to IQOS use and patients who continue to smoke CC. The growth rate is calculated as the slope of the linear regression fit to the maximum minor-axis AAA diameter values over the time by randomization arm.

Descriptive statistics for maximum minor-axis AAA diameter will be summarized at each visit and overall (across all patients). The primary endpoint will also be summarized by strata (maximum-minor-axis AAA diameter, CC consumption, sex).

Study evaluation criterion:

This is a descriptive study, designed to gain an understanding on the effect of complete switching from cigarettes to IQOS use compared to continued CC smoking on the AAA growth rate and disease progression. Dual use of IQOS on top of CC will be also investigated. There are no formal statistical hypotheses to be tested.

Evaluation Criteria:

No formal evaluation criterion is applied since this is a descriptive study.

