9 PLANNED STATISTICAL METHODS

9.1 General Considerations

9.1.1 Stratified Presentation

As described in Section 7, stratified analyses will not be conducted as part of this SAP.

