9.5 Planned Statistical Analyses

9.5.1 Primary Analyses

9.5.1.1 Mean Growth Rates

Summary of the Annualized Mean Growth Rates in Patients Diagnosed with AAA		
Population	:	FAS
Group	:	
• Study arm• Product Use Category
Contents	:	
The primary endpoint is the comparison of the annualized mean growth rates of AAA diameter between patients who were randomized to IQOS use and patients who continue to smoke CIG. The growth rate is calculated as the slope of the linear regression fit to the maximum minor-axis AAA diameter values over the time by randomization arm.
 
Descriptive statistics for the annualized mean growth rates of AAA will be presented.

Target visit	:	V3 to V8
Sample code	:	Linear regression

$$\text{Study Day} = \text{Measured date of visit} - \text{measured date of Baseline} + 1$$

Confidentiality Statement

Data and information contained in this document are considered to constitute trade secrets and confidential commercial information, and the legal protections provided to such trade secrets and confidential information are hereby claimed under the provisions of applicable law. No part of this document may be publicly disclosed without the written consent of Philip Morris Products S.A.

Summary of the Annualized Mean Growth Rates in Patients Diagnosed with AAA

	<pre>proc reg data = TargDs outest=outds ; by subject; model AAA diameter = Study day ; ods output ParameterEstimates = out1; run ;</pre>
Output	
Summary of the Annualized Mean Growth Rates in Patients Diagnosed with AAA -FAS-
 
Summary of the Annualized Mean Growth Rates in Patients Diagnosed with AAA by Product Use Category -FAS-
 
Figure of the Annualized Mean Growth Rates in Patients Diagnosed with AAA -FAS-
 
Figure of the Annualized Mean Growth Rates in Patients Diagnosed with AAA by Product Use Category -FAS-
 
Listing of Maximum minor-axis AAA Diameter Growth
 
Listing of Statistical Output (REG procedure)
 
Listing of Statistical Output (REG procedure) by Product Use Category

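### With the stratified analyses cancelled, the primary growth-rate comparison has no adjustment for baseline diameter or sex, leaving avoidable confounding in the two non-randomised smoking-cessation contrasts

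*SAP*

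**What the plan says.** Protocol 12.1.1 names diameter (cut at 40 mm in men and 35 mm in women) and sex, and states: "For the primary analysis of AAA annual growth rate, the following stratification criteria will be used". Of the SC patients, who are not randomised, it adds that "they will be analyzed based on the defined stratification criteria". Protocol 12.6 gives the form this takes: "The primary endpoint will also be summarized by strata (maximum-minor-axis AAA diameter, CC consumption, sex".

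The protocol's reasons are prognostic. Section 2.1 says that "a larger aneurysm size at diagnosis indicates a more rapid expansion of the aneurysm further on", and section 4.1 cites "sex differences in terms of growth rate and indication for open surgical AAA treatment or AAA endovascular repair".

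SAP 7 withdraws the stratified analyses because "the expected number of subjects in each stratum will be too small to draw any conclusion. Thus, stratified analyses will not be conducted", and SAP 9.1.1 repeats it: "As described in Section 7, stratified analyses will not be conducted as part of this SAP". SAP 9.5.1.1 then fits, for each patient, "model AAA diameter = Study day" over V3 to V8 and gives descriptive statistics of the slopes by study arm and by product use category. It has no covariate, and it defines no between-arm difference or interval.

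The primary objective (Protocol 3.1, SAP 3.1) contains three contrasts: IQOS versus cigarettes, IQOS versus SC, and cigarettes versus SC. Only the first is randomised (Protocol 6.4).

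**The concern.** Small strata are a good reason not to print results stratum by stratum. They do not stand in the way of a model with one or two main-effect covariates. The SAP already adjusts at this sample size elsewhere: the biomarker model in SAP 9.5.2.2 includes the log baseline value and starts from an unstructured covariance over six visits, which is 6 × 7 / 2 = 21 covariance parameters. The primary growth endpoint gets no baseline term.

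What is at stake differs by contrast. Stratified randomisation protects IQOS versus cigarettes against imbalance in diameter and sex. Nothing does so for the SC arm. If ex-smokers enter with larger or smaller aneurysms, and larger aneurysms grow faster, part of the difference in mean slope reflects starting size and would be read as an effect of smoking status.

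**Working it through.** The plan gives no SD, power, effect size or sample-size calculation, so there is no figure of its own to reproduce. Values marked as assumed are not in the documents.

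**1. Is the SAP's reason sound?** Protocol 4.4 reports 32 patients enrolled and a forecast of 15 more, so 32 to 47 at most. Three arms by four strata is 12 cells: 32/12 = 2.7 and 47/12 = 3.9 patients per cell. Stratum tables would indeed be uninformative. Two covariates use two degrees of freedom, not twelve cells.

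**2. Confounding in the SC contrasts.** Bias = (growth per mm of starting diameter) × (difference in mean starting diameter). With assumed inputs, in mm/year:

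| Growth per mm (mm/year) | 1 mm difference | 3 mm | 5 mm |
|---|---|---|---|
| 0.02 | 0.02 | 0.06 | 0.10 |
| 0.08 | 0.08 | 0.24 | 0.40 |
| 0.15 | 0.15 | 0.45 | 0.75 |

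The reference is the difference of about 0.4 mm/year in Protocol 2.1. To match it, a 5 mm difference needs 0.4/5 = 0.08 mm/year per mm, a 3 mm difference 0.4/3 = 0.13, and a 1 mm difference 0.40, which is outside the assumed range.

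Differences of this order need no selection effect. Men are eligible from 30 to 49 mm. If diameters are uniform over that range (assumed), the SD is 19/√12 = 5.5 mm. With 32/3 = 10.7 per arm (equal thirds assumed), the standard error of a difference in means is 5.5 × √(2/10.7) = 2.4 mm.

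**3. The randomised contrast.** I simulated 1:1 randomisation in blocks of 4 within the protocol's strata. Assumptions: 21 randomised (two thirds of 32), 15% women, uniform diameters, residual slope SD 1.5 mm/year. Variance explained is (5.48b)² / [(5.48b)² + 1.5²], where b is growth per mm. Ratios are adjusted over unadjusted:

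| b | Variance explained | CI width, diameter only | CI width, diameter and sex | True SD of estimate, diameter only |
|---|---|---|---|---|
| 0 | 0% | 1.01 | 1.03 | 1.01 |
| 0.05 | 3% | 1.00 | 1.02 | 1.01 |
| 0.10 | 12% | 0.95 | 0.97 | 0.99 |
| 0.15 | 23% | 0.89 | 0.90 | 0.96 |

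Unadjusted coverage rises from 95% to about 97% down the table. Most of the narrowing is therefore removal of conservatism; the estimate's true SD falls by at most about 4%. With 31 randomised the pattern is the same.

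**4. Cost in the SC contrasts.** If diameter is unrelated to growth, adjusting for a difference Δ multiplies the interval width by about √{1 + (n/2)Δ² / [(N−3)s²]}. With n = 10.7, N = 32, s = 5.48 and Δ = 5 this is √{1 + 5.33 × 25 / (29 × 30.1)} = √1.15 = 1.07. With Δ = 3 it is 1.03.

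**The case against.** The strongest reply is that SAP 7 dropped no adjustment. Protocol 12.6 planned summaries by strata, neither document contains a covariate-adjusted growth model, and SAP 7 is open about cancelling summaries that cells of three or four patients cannot support. This largely stands. A reader might infer that the SAP abandons a prespecified adjusted analysis, but Protocol 12.1.1 is at most ambiguous on that. A reader might also infer that the strata disappear altogether. They do not: they remain in the randomisation (SAP 4.3.1.1), and the baseline table (SAP 9.3) shows sex and the diameter categories by arm, so an imbalance in SC would be visible, though not corrected.

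Second, it may seem that the randomised comparison loses material precision. The documents do not support this. Stratification already balances diameter, the variance explained is unknown, and the SAP defines no between-arm interval that could be too wide.

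Third, the comparison named in Protocol 12.6 and SAP 9.5.1.1 is IQOS versus cigarettes only, all arms share the diameter limits and the documented-growth requirement, and the protocol's statement on size concerns size at diagnosis, not at V1. These points soften the concern without removing it. The SC contrasts are in the primary objective, the SC slopes will be tabulated beside the others, and the eligible range in men still spans 19 mm.

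Fourth, the bias figures multiply two assumed ranges. That is correct; they show scale and are not estimates.

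**Conclusion.** The point holds as an improvement to the analysis of the primary endpoint, chiefly for the two SC contrasts. The decision against stratum tables is sound. Its reason does not extend to leaving out two recorded factors that the protocol itself calls prognostic.

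Under the stated assumptions, unadjusted confounding by diameter runs from negligible (0.02 mm/year) to larger than the cited 0.4 mm/year difference (0.75 mm/year). It matches that difference only towards the upper end of both assumed ranges. For IQOS versus cigarettes, adjustment changes the interval from about 1-3% wider to about 10% narrower and adds little real precision. The number per arm, the share of women, the slope SD, the growth-diameter relation and any baseline difference are not in the documents.

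Adjustment would deal with diameter and sex only. Other differences between ex-smokers and smokers would remain, and reading error in the V1 scan would make the diameter adjustment incomplete.

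**What to change.** Keep the decision in SAP 7 not to print stratum tables. In SAP 9.5.1.1 add a linear model of the per-patient annualised slope on study arm (three levels) and the centrally read V1 diameter as a continuous covariate. Add sex as a separate term if enough women are enrolled, by a rule written down before the growth data are seen. Report adjusted arm means and the three arm differences with 95% CIs beside the unadjusted ones; this also supplies the between-arm estimate that the SAP lacks. Label the SC contrasts as non-randomised and adjusted only for diameter and sex (or diameter alone, if sex is left out).

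Do not replace the two terms by a single diameter centred at each sex's cut-off. Diameter minus 40 in men and minus 35 in women forces the sex effect to equal five times the diameter slope (0.5 mm/year at 0.10 per mm), which nothing in the documents supports.

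The V1 diameter is already collected and is not among the V3 to V8 values that form the slope. The cost is one SAP paragraph, one model and one or two degrees of freedom. If diameter proves unrelated to growth, the randomised interval is about 1-3% wider and an SC interval up to about 7% wider with a 5 mm imbalance. If the database is already locked, SAP section 1 allows this as an additional analysis described in the study report, where it should be labelled post hoc.
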